Primary outcomes: Increased peak isokinetic muscle torque output as measured using a Biodek machine of the shoulder internal rotators, external rotators, shoulder abductor/adductors, and shoulder flexion/extension, elbow flexion/extension, forearm pronation/supination, wrist flexion/extension, and hand grip measured using a handheld dynamometer at 6 weeks (mid-way into training) and 12 weeks (end of training) when compared to baseline.

Secondary outcomes:

- o Propulsion testing: Increased maximum speed and acceleration attained, peak force, and mechanical effective force measured using the SmartWheel during start-up propulsion over level and inclined surfaces at 12 weeks when compared to baseline
- o Transfer testing: Higher maximum and minimum attainable transfer heights to a height-adjustable transfer station at 12 weeks when compared to baseline;
- o Reduced upper limb pain across all joints (as recorded on the Numerical Rating Scale (NRS) and shoulder pain reported during activities (Wheelchair Users Shoulder Pain Index (WUSPI)) at 6 weeks and 12 weeks when compared to baseline;
- o Increased self-perceived aspects of health and function as measured using the Short Form SF-36 Walk Wheel scale at 6 weeks and 12 weeks and when compared to baseline.
- o Increased peak power and average power output at 12 weeks compared to baseline.

Specific Aim 2) Assess subjects' perceptions of the effectiveness of the vibration dumbbell training program

Hypothesis 2) Subjects will report a high level of satisfaction with the training on factors of efficiency, tolerance, perceived strength and functional benefits.

Study Design and Methods

Each subject will be asked to come to HERL three times over a 12-week study period. During these visits the following activities will take place a) Pain and Health Surveys (Baseline and Weeks 6, and 12), b) Muscle Strength Testing (Baseline and Weeks 6 and 12), c) Functional Testing (Baseline and Week 12), and Pre-Training Assessment and Instructions (Baseline). The 12-week Training Phase will start after Visit 1

Data will be collected electronically using redcap, or on paper as needed.

Visit 1 (Initial Visit)

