If subjects successfully complete the vibration screening they will continue with the following assessments during Visit 1:

General Health and Function: The 36-Item Short Form Health Survey Walk Wheel (SF-36 WW) is a slightly modified version of the original SF-36 that has been validated for persons with SCI. The SF-36 is a brief, multi-dimensional, self-report health questionnaire that measures eight concepts - Physical Functioning,

Role limitation due to Physical problems, Bodily Pain, General Perception of Health, Vitality, Social Function, Role limitation due to Emotional problems, and Mental Health. The domain scales ranges from 0 (worst possible health state measured by the questionnaire) to 100 (best possible health state).

Power output: the Lode Arm Ergometer will be used to measure the maximum power output for each participant. This test will be done with the participant seated in their wheelchair. The arm ergometer height will be adjusted such that participants are able to comfortably reach and crank both pedals. Additionally, we will want subjects to be in a stable participation. If they are able to, participants should brace their feet on their foot plate. If a participant does not feel enough stability in their wheelchair we will have a stable chair for them to transfer to in order to perform the evaluation. Participants will start out by cycling on the arm ergometer at a comfortable pace as a warm up. Once the participant feels as though they are sufficiently warmed up the test will begin. Participants will begin cycling against maximum resistance. Once that happens participants will be instructed to cycle as hard and as fast as they can for as long as they are able to. Once they are no longer able to crank against the resistance the test will stop and the maximum resistance will be recorded. We will complete this process three separate times, with a minimum of 30 seconds of rest in between. After the test is completed, the resistance will return to zero and the participants will cycle at a comfortable pace to cool down. They will cycle as long as they need to in both the warm up and cool down phases.

Muscle Strength Testing

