At the end of the 12-week intervention period, subjects will come back to the lab for the final visit. This visit will be scheduled 12-14 weeks after the start of the intervention. However, even if a participant is unable to come back at 12 weeks exactly, the exercise program will still end at 12 weeks.

The follow-up visit intake form will be completed to identify any changes in the participants health or medical status, lifestyle or any other changes that could impact the participants ability to complete the exercise program. At this visit subjects will complete all the measures that were completed during the first visit. This includes the pain measures, measure of health and function, carpal tunnel questionnaire, strength, power output and functional measures. These tasks are expected to take up to 5 hours to complete.

As stated above, three exercise sessions will be scheduled each week. We expect that this schedule will be modified due to scheduling conflicts, illness, etc. and it is possible that subjects may sometimes complete less than three visits per week. All visits that are changed or missed will be documented in the research record but will not be considered protocol deviations so long as they are completing a minimal number of sessions (10) per six-week period. If a subject completes less than 10 exercise sessions in a 6-week period they will be removed from the study.

As stated above, testing sessions at the HERL lab will be scheduled at 6 and 12 weeks from the baseline visit. We expect that this schedule will be modified due to scheduling conflicts, illness, etc. For this reason, subjects will be given a 2-week window (6-8, 12-14 weeks) in which to complete these visits. Testing sessions within this window will not be considered protocol deviations.

Eligibility Criteria

Inclusion Criteria:

- (1) have a neurological impairment secondary to a SCI or disease at T2 or lower
- (2) greater than 6 months post injury
- (3) use a manual wheelchair as primary means of mobility (at least 30 hrs. per week)
- (4) 18 to 65 years of age
- (5) provide signed medical release by primary care physician to engage in a high-intensity resistance training exercise program
- (6) live within 60 minutes driving time (1 hour) from the research center
- (7) able to perform a transfer independently to and from a wheelchair
- (8) have normal range of motion in the upper limbs.

Exclusion Criteria:

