- (1) history of fractures or dislocations in the shoulder, elbow and wrist from which the subject has not fully recovered or joint replacement of any of the joints in the upper extremities
- (2) upper limb pain that interferes with the ability to propel or transfer
- (3) recent hospitalization for any reason (within the past three months)
- (4) pregnant women
- (5) history of coronary artery disease, coronary bypass surgery or other cardiorespiratory events

Statistical Plan

Distributions of all data will be examined. Should outliers or distributions that are nonlinear in nature be present, appropriate transformations will be performed. Means and standard deviations, or medians and ranges, as appropriate, will be calculated for all variables. A repeated measures ANCOVA will be used to examine primary (strength) and secondary outcome measures (pain, quality of life, power, transfer ability, propulsion characteristic) for the three time points. For significant models, post-hoc analyses with Bonferroni corrections will be used. Total number of training sessions completed will be entered as a covariate if necessary. The training progress (e.g. hold times) and training adaptations made and documented by the trainer during each session will be analyzed using graphical methods to further assess training effects that occur overtime.

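### The arm-ergometer procedure records only maximum resistance, which cannot yield the peak and average power named as secondary outcomes

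*Combined protocol and SAP*

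**What the plan says.** The list of secondary outcomes under Specific Aim 1 includes "Increased peak power and average power output at 12 weeks compared to baseline". The Power output paragraph for Visit 1 opens with a matching purpose: "the Lode Arm Ergometer will be used to measure the maximum power output for each participant". The procedure then runs as follows.

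- Load: after a warm-up, "Participants will begin cycling against maximum resistance".
- Effort: subjects are told to "cycle as hard and as fast as they can for as long as they are able to".
- End and record: "Once they are no longer able to crank against the resistance the test will stop and the maximum resistance will be recorded".
- Repetition: "We will complete this process three separate times, with a minimum of 30 seconds of rest in between".

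Afterwards the resistance goes back to zero for a cool-down. The Visit 3 section repeats the test by name only: "This includes the pain measures, measure of health and function, carpal tunnel questionnaire, strength, power output and functional measures". The Statistical Plan lists power among the "secondary outcome measures (pain, quality of life, power, transfer ability, propulsion characteristic) for the three time points" and defines no variable. (Power is scheduled only at baseline and week 12. The reference to three time points is a separate matter and is not pursued here.)

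Two smaller items sit in the same list of secondary outcomes. The transfer hypothesis expects both the maximum and the minimum attainable height to be higher at week 12. The propulsion hypothesis expects greater maximum speed and acceleration, peak force and mechanical effective force on level and inclined surfaces.

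**The concern.** The named outcomes, the stated purpose of the test and the stated record do not match. Two outcomes are powers, and the purpose is a maximum power. The record is a resistance, and the same term describes the starting condition and the result. Average power does not appear in the procedure at all.

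Other tests in the protocol do not have this problem. Muscle Strength Testing records torque for a torque outcome, and Transfer Assessment records heights for a height outcome.

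At stake is whether the two power outcomes can be computed from what staff are told to write down. If the device does supply power, a second question is whether the trial used and the averaging period are fixed before the data are seen. The primary strength outcome is not touched.

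**Working it through.** The documents give no torque, cadence, trial duration, power value or trial variability, so there is no plan figure to reproduce. The check is a comparison of texts, followed by illustrations on assumed inputs.

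**1. Named outcome against recorded value**

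| Item | Specific Aim 1 | Power output procedure |
|---|---|---|
| Peak power | named | stated as the purpose (maximum power); not listed as recorded |
| Average power | named | not mentioned |
| Resistance | not an outcome | the only recorded value |
| Cadence, torque, work, duration | not mentioned | not mentioned |
| Rule for combining three trials | not mentioned | not mentioned |

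The Visit 3 section and the Statistical Plan fill none of these gaps.

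**2. Resistance does not determine power**

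Power (W) = torque (N·m) × 2π × rpm / 60. Torque and cadence are assumed.

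| Torque | 60 rpm | 90 rpm |
|---|---|---|
| 10 N·m | 62.8 W | 94.2 W |
| 20 N·m | 125.7 W | 188.5 W |
| 30 N·m | 188.5 W | 282.7 W |

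Within each row the recorded resistance is the same, while power differs by the cadence ratio, 90/60 = 1.5.

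**3. Average power depends on the averaging rule**

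Suppose power falls linearly from an assumed 200 W to 0 W at failure time T: P(t) = 200(1 − t/T). A subject moves from T = 20 s at baseline to T = 25 s at week 12.

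- Whole-trial mean: 200/2 = 100 W for any T, so the change is 0%.
- Fixed window W with zero power after failure, m = min(T, W): mean = (200m − 200m²/(2T))/W.
 - W = 20 s: 100.0 W, then (4000 − 1600)/20 = 120.0 W, a change of +20%.
 - W = 30 s: 2000/30 = 66.7 W, then 2500/30 = 83.3 W, a change of +25%.

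**4. Combining three trials**

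For three independent normal trials the expected maximum exceeds the mean by 3/(2√π) = 0.846 SD. With an assumed within-subject SD of 5% to 10% of the mean, the best trial averages 4.2% to 8.5% above the mean of three, ignoring fatigue. Most of this cancels in a change score if one rule is used at both visits.

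**5. The smaller items**

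- Transfer: the Background aims at reaching higher and lower surfaces, and Transfer Assessment finds how low the subject can go. A lower minimum is therefore the improvement, whereas the hypothesis literally asks for a higher one.
- Propulsion: in the Wheelchair Propulsion Assessment only the level runway is run up to maximum velocity. All ramp trials are at a comfortable pace, so ramp measures depend partly on the pace chosen.

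**The case against.** The strongest reply is that the procedure opens by saying the device measures maximum power, so the recording sentence may be a loose term for that maximum, and the ergometer may log power anyway. This stands in part. Peak power is the declared purpose, and the firmest gap is average power. But a recording instruction should be correct when followed literally, and this one is not.

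A reader might go further and infer that the power data are lost. The documents do not support that, because they are silent on what the device stores. A reader might also infer that the recorded change must be zero, since the load is both the start and the result. That would follow only if the resistance is preset and identical at both visits, and the documents do not say how it is set.

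It is also fair to say that every figure above rests on assumed inputs. The averaging example was built so that only endurance improves. With an open-ended test, the whole-trial mean is a natural reading of average power. The example shows that the choice can matter, not how much it matters in this trial. Which trial to use, which window, and how to treat early failure are missing details on which reasonable people differ.

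On ramps, maximum speed attained can mean the highest value within a comfortable-pace trial, and each trial is timed with exertion recorded. That item is a mismatch in labelling rather than a clear contradiction. The transfer item is a slip of direction that changes no data or test statistic.

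**Conclusion.** The point holds as an error in the written recording rule. Followed exactly, the procedure produces a resistance from which neither peak nor average power can be computed, and average power has no described measurement. This conclusion needs no assumed number, only the relation between power, torque and cadence.

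Its reach is limited to secondary outcomes in a study whose stated purpose is exploratory. How much the error would distort a result cannot be sized from the documents. It should be fixed because the stated rule is wrong and cheap to correct. The transfer and ramp items carry less weight and do not raise the severity.

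**What to change.** In the Power output procedure:

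- Replace the instruction to record maximum resistance with peak power and mean power in watts for each of the three trials. If the device does not output watts, record cadence together with the set resistance so that power can be derived.
- State how the test resistance is set, and use the same rule at baseline and week 12.
- State one rule for combining the trials and one averaging rule, including how a trial that ends early is handled. Apply both at both visits. The choice is the sponsor's; what matters is that it is fixed before the data are seen.

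In the secondary outcomes under Specific Aim 1:

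- Word the transfer hypothesis as a higher maximum and a lower minimum attainable height.
- Reconcile the propulsion hypothesis with the Wheelchair Propulsion Assessment by labelling the ramp measures, including the force measures, as comfortable-pace outcomes.

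The cost is wording, plus saving a power or cadence signal from trials already planned, assuming the ergometer outputs one. No extra visit or procedure is needed.

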training upper limb muscle force and power. For any subject who begins training at 30 Hz, the frequency will be reassessed at each training session to progressively increase him/her (in increments of 5 Hz) to 40 Hz.

The vibrating dumbbell, without added weights, weighs 6 pounds. It is possible that early in the exercise program a subject in the vibration intervention group may not be able to properly perform a specific exercise with that weight. In this case the subject will perform the exercise with a lighter weight standard dumbbell until they increase sufficiently in strength.

Visit 1 will take up to 5 hours to complete.

Optimally, each subject will be scheduled for three training sessions per week in their home for 12 consecutive weeks. Although the home was chosen for the training setting to make it easier on subjects to comply with the protocol, training can take place in another location based on subject convenience. The training equipment is portable and can be easily setup and broken down after each session. All the training for both the control and vibration groups will be supervised by a trainer with appropriate knowledge of proper exercise form and safety. The trainer will travel to the agreed upon location and guide the subject through each training session. The training sessions will be monitored by a physical therapist (PT). Both the trainer and PT will be masked to subjects' performance on outcome measurements.

Prior to beginning each exercise session, female subjects will be reminded that they should not participate in vibration exercise activities if they are pregnant and should notify the study team if they think they could be. Female subjects will be asked weekly if they are or could be pregnant and this will be documented. If pregnancy is a possibility, the subject will be offered an over the counter pregnancy test. Subjects will be given the test to perform themselves, unless they are physically unable to because of disability related functional limitations. In these circumstances, a female staff member will assist as needed. Any subject reporting or testing positive for pregnancy will be withdrawn from the study.

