use another surface in their home for these exercises if it is determined to be safe and appropriate by the trainer or other member of the study team. For the rest of the exercises, subjects will exercise while in their wheelchair. A lap belt will be provided to subjects who do not have one and will be used to secure their pelvis in the wheelchair and to provide a more stable base of support while exercising. Emphasis will be placed on maintaining a neutral thoracic and cervical posture and avoiding scapular elevation during seated exercises. Depending on the amount of trunk control present, subjects may use their opposite limb to brace their trunk (either forearm pressed against their thighs or placed on an adjacent table) for exercises involving forward trunk flexion (e.g. bent over rows, triceps extensions and side flies). Verbal cuing and spotting from the trainer will be provided during the sessions to monitor positioning and safety with the exercises.

The trainer will only facilitate and supervise the exercise training. The trainer who will be conducting the training sessions will guide the subjects through each exercise set and ensure that the correct weights, timing, vibration frequency, arm postures and technique are being used to maximize subject safety. He/she will also perform survey-based data collection and research procedures. Training procedures will be stopped immediately by the trainer if a subject complains of pain or extreme discomfort during the exercises. The subject will be instructed to check in with his/her physician before resuming training.

The trainer will reassess the intensity of the training parameters at the end of each session and adapt as necessary. He/she will keep a training log for each subject and session that documents the training parameters (e.g. hold times completed each session), total session duration time, and changes made to increase/decrease efforts for the next session. Health parameters, such as heart rate and blood pressure will be collected. An automatic blood pressure monitor will be placed on the upper arm of the subject to measure their blood pressure. An automatic pulse ox monitor will be placed on the finger of the subject to measure their heart rate. The trainer will also take general notes on the sessions and the exercises, as well as the plan for the next exercise session.

Each training session is expected to take up to 1.5 hours.

Training Intensity Assessment and Adjustments

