Training intensity will be adjusted progressively with add-on dumbbell weights that will be added to the vibrating dumbbell. Subjects will be asked to hold onto the vibrating dumbbell tightly for as long as they can for each exercise. If they are unable to hold on tightly for at least 15 seconds, the weight for the next session will be decreased, whereas if they are able to hold onto the dumbbell for greater than 60 seconds, the trainer will stop the exercise and the dumbbell weight will be increased for the next session. The amount of weight increased and decreased will be determined by the trainer and will be reviewed and verified by a member of the senior study personnel.

The trainer will meet with the senior study personnel (PT and PI) at minimum once a week to review subjects' training progress, performance, any complications, concerns or complaints that the subject expresses, and any changes in the health status of the subjects who had been seen over the course of the week. Senior personnel will re-assess and modify the training procedures as appropriate.

During the last week of training (week 12), the trainer will give subjects a survey to assess satisfaction with the training program to collect their feedback on factors such as tolerance, perceived strength, performance and health benefits, efficiency of training, choice to continue training, and if they would recommend this form of exercise to others.

The follow-up outcome assessment visit, which take place at our laboratory, will be conducted by the PhD student and overseen by the PI.

Visit 2 (midway visit)

Participants will come back to the lab 6-8 weeks from the beginning of the intervention. The follow-up visit intake form will be completed to identify any changes in the participants health or medical status, lifestyle or any other changes that could impact the participants ability to complete the exercise program. At this visit we will test their strength in the same way that it was tested on initial visit. Additionally, they will fill out the pain measure forms, the health and satisfaction form and the carpal tunnel questionnaire that were filled out at the first visit.

This visit is expected to take no more than 2 hours to complete.

Visit 3 (end of the exercise program)

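### The Aim 2 satisfaction survey is handed out by the trainer with no described safeguard, and the trainer's wider survey role is left undefined

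*Combined protocol and SAP*

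**What the plan says.** Four statements bear on the trainer's part in data collection.

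- **Masking.** The training description that follows the Functional Testing text of Visit 1 states: "Both the trainer and PT will be masked to subjects' performance on outcome measurements".
- **Duties.** Later in the same description: "The trainer will only facilitate and supervise the exercise training". Two sentences on, about the same person: "He/she will also perform survey-based data collection and research procedures". The surveys are not named.
- **Satisfaction survey.** Training Intensity Assessment and Adjustments states: "During the last week of training (week 12), the trainer will give subjects a survey to assess satisfaction with the training program". The topics listed there match those of Hypothesis 2 under Specific Aim 2: "Subjects will report a high level of satisfaction with the training on factors of efficiency, tolerance, perceived strength and functional benefits".
- **Follow-up testing.** The same section states: "The follow-up outcome assessment visit, which take place at our laboratory, will be conducted by the PhD student and overseen by the PI".

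The opening of Study Design and Methods puts the pain and health surveys at the laboratory visits and provides for data capture in REDCap, with paper as a fallback.

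**The concern.** Aim 2 asks what subjects think of the programme. The person who delivers it, usually in the subject's home, also hands over its evaluation while training is still under way. Subjects who have worked with a trainer for three months may be reluctant to say to that person's face that the programme was inefficient, hard to tolerate or of little benefit. Any such reluctance pushes answers toward Hypothesis 2.

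Nothing later in the plan would reveal or offset this. Hypothesis 2 sets no threshold for high satisfaction, and the Statistical Plan names no analysis for it. The training description mentions a control group, but neither the hypotheses nor the Statistical Plan contains a between-group comparison.

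The second issue is the wording of the duties. A reader cannot tell which surveys the trainer may collect, and therefore cannot tell whether the masking statement is respected.

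**Working it through.** The plan states no figure on this point. The check is a comparison of the text plus one count of contact.

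**1. Contact with the trainer before the survey**

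- Planned: 3 sessions per week × 12 weeks = 36 (training description).
- Minimum to remain in the study: 10 sessions per six-week period × 2 periods = 20 (Visit 3).

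The survey is given during week 12, so a few of these sessions may come after it. The documents do not say whether one trainer sees a subject throughout. The counts measure exposure to the trainer's supervision; they do not measure bias.

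**2. Does Aim 2 depend on this survey?**

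The week-12 survey covers tolerance, perceived strength and other benefits, efficiency, and willingness to continue and to recommend. Those include the factors in Hypothesis 2. Visit 2 mentions a form on health and satisfaction said to have been filled out at Visit 1, but no satisfaction instrument is described at Visit 1. The trainer-given survey is therefore the only Aim 2 instrument with described content.

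**3. Is a safeguard described?**

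No. The text does not mention anonymity, a sealed return, restricted access or collection by someone outside the training.

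**4. Do the trainer statements agree?**

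| Pair | Result |
|---|---|
| *Only* training against *also* surveys | Conflict as worded |
| Masking against giving the satisfaction survey | No conflict: satisfaction is not among the primary or secondary outcomes under Specific Aim 1 |
| Masking against the unnamed surveys | Conflict only if they include the NRS, WUSPI, SF-36 WW or carpal tunnel forms |

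**5. Are the outcome questionnaires likely to be among the unnamed surveys?**

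The visit schedule, Visit 2 and Visit 3 place them at the laboratory, and follow-up assessment is assigned to the PhD student. That points away from the trainer. It does not settle the matter: the survey duty has no stated limit, and the documents do not say that the PhD student and the trainer are different people.

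**The case against.** The strongest reply is that the three trainer statements can be read together without difficulty. The one survey that the documents assign to the trainer is the satisfaction survey. It rates the programme rather than the trainer, it is not a listed outcome, and giving it out does not mean watching it being completed or reading the answers. Aim 2 is descriptive, and the primary outcome, strength, does not depend on it.

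Much of this stands. It limits the point to Aim 2 and to unclear wording. It does not remove the point, because the programme's evaluation still passes through the person who delivers it, with nothing to reassure the subject.

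A reader might infer three stronger things that the documents do not support:

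- **That the pain, health and carpal tunnel results are biased by trainer collection.** Nowhere is the trainer said to administer those forms. They belong to the laboratory visits, and subjects fill them out themselves.
- **That the masking is breached.** That would require the trainer to collect or see outcome questionnaires, which is possible under the open wording but not stated.
- **That survey answers would steer training loads.** The text ties weight changes to hold time and has senior personnel verify them. The trainer is in any case expected to hear complaints during sessions and report them.

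**Conclusion.** The point holds for Aim 2. The satisfaction survey is given by the trainer after up to 36 supervised sessions, with at least 20 required over the full period, and no safeguard is described. Answers are therefore open to courtesy bias in the direction of Hypothesis 2. The direction is a judgement about how people answer in this setting. The size cannot be estimated: the documents give neither a response scale nor any data on it.

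For the pain, health and carpal tunnel questionnaires the finding is narrower. The wording of the trainer's duties contradicts itself and leaves trainer involvement open, while the visit schedule and the assignment of follow-up testing suggest otherwise. That calls for clarification and is not evidence of bias in those outcomes.

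This is a cheap improvement. It does not threaten the primary outcome.

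**What to change.** 1. In Training Intensity Assessment and Adjustments, have subjects complete the satisfaction survey themselves in week 12 through a REDCap link, or on paper in a sealed return. Give the trainer no access to individual answers, and tell subjects so before they respond. Keeping it in week 12 avoids the delay that a move to Visit 3 could bring, since that visit may fall as late as week 14.
2. In the description of the trainer's duties, limit data collection to the training log, the session health parameters and the safety information already planned. This removes the conflict between *only* and *also*.
3. State that the trainer neither administers nor sees the NRS, WUSPI, SF-36 WW or carpal tunnel forms, so that the duties agree with the masking statement.

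The cost is wording and REDCap access settings. Item 1 needs no extra staff. Item 3 needs none if the PhD student and the trainer are different people, which the protocol should confirm. The downside is a possibly slightly lower survey return than when the form is handed over in person.
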